 - When the findings from a chest CT-scan less than 12hours old are available;
 - For each clinical hypotheses;
 - For each level of certainty of clinical hypothesis;
 - For type of patients (reasons for admission the most represented);
 - For each research center.
2. Determine the level of agreement between the physiotherapist's diagnosis comparing the clinical vs LUS findings, overall, for the level of certainty of clinical diagnosis and for the population where a CT-scan is available;
3. Determine the frequency of changes in the chest physiotherapy following the assessment of the LUS results, overall and for each type of clinical hypothesis;
4. Determine the frequency of changes in the medical treatment (determined by intensivist) following the assessment of the LUS results performed by the physiotherapist, overall and for each type of clinical hypothesis.

4. Judgement criteria

4.1.Principal judgement criterion

Modification of the clinical decision: agreement (yes/no) between the lung and diaphragm US diagnosis and the clinical diagnosis and modification (yes/no) of the chest physiotherapy protocol, expressed using the Net Reclassification Index (NRI).

4.2.Secondary clinical decision-makingjudgementcriteria

1. Modification of the clinical decision:
 - When a chest CT-scan < 12h is available;
 - For each clinical hypotheses;
 - For the level of certainty of clinical hypotheses (Likert scale: strongly certain, certain, neither certain nor uncertain, uncertain, strongly uncertain);

- For type of patients (reasons for admission the most represented);
 - For each research center.
2. Proportion of agreement between clinical and LUS diagnosis:
- Overall;
 - For the level of certainty of clinical hypotheses (Likert scale: strongly certain, certain, neither certain nor uncertain, uncertain, strongly uncertain);
 - When chest CT-scan < 12h is available.
3. Proportion of cases when the chest physiotherapy protocol is modified following the results of the LUS:
- Overall;
 - For each type of clinical hypothesis;
 - When a chest CT-scan < 12h is available;
4. Modification of the clinical decision of intensivist:
- Overall;
 - For each type of clinical hypothesis;
 - When a chest CT-scan < 12h is available.

5. Inclusion/exclusion criteria:

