8.2. Statistical method

8.2.1. Modification of the clinical decision chest physiotherapy

Calculation of the net reclassification index (NRI) (29):

$$\text{NRI (\%)} = (P_{\text{upevents}} - P_{\text{downevents}}) - (P_{\text{upnonevents}} - P_{\text{downnonevents}})$$

With:

Events: the results of the lung and diaphragm US are compatible with the clinical diagnosis for a clinical hypothesis.

Non Events: the results of the lung and diaphragm US are not compatible with the clinical diagnosis for a clinical hypothesis.

P_{upevents}: number of «events» when the LUS results modified the chest physiotherapy treatment modalities divided by the total number of «events».

P_{downevents}: number of «events» when the LUS results didn't modify the chest physiotherapy treatment modalities divided by the total number of «events».

P_{upnonevents}: number of «non-events» when the LUS results modified the chest physiotherapy treatment modalities divided by the total number of «non-events».

P_{downnonevents}: number of «non-events» when the LUS results didn't modify the chest physiotherapy treatment modalities divided by the total number of «non-events».

The significance test used will be the correlated proportions test (use of the properties of multinomial distribution). This is an asymptotic test for the hypothesis $NRI=0$.

$$z = \frac{\widehat{NRI}}{\sqrt{\frac{\hat{p}_{up,events} + \hat{p}_{down,events}}{\# \text{ events}} + \frac{\hat{p}_{up,nonevents} + \hat{p}_{down,nonevents}}{\# \text{ nonevents}}}}$$

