8.2.3. Agreement between clinical and LUS diagnosis

Calculation of Kappa index:

The clinical diagnosis and the lung ultrasound allow to diagnose the following events : (the retained airway secretions and bronchospasm diagnoses aren't included in the analysis as LUS doesn't allow their diagnosis (LUS may only be compatible with these hypotheses):

- T1: pneumonia/consolidation;
- T2: atelectasis (~~passive or active mechanism~~ obstructive);
- T3: pleural effusion;
- T4: pulmonary edema or global interstitial syndrome;
- T5: pneumothorax;
- T6: reduced aeration at the most dependent parts of the lungs;
- T7: diaphragm dysfunction (unilateral or bilateral);
- T8: examination is inconclusive.

Contingency table:

		Lung ultrasound								Total
		T1	T2	T3	T4	T5	T6	T7	T8	
Clinical diagnosis	T1									
	T2									
	T3									
	T4									
	T5									
	T6									
	T7									
	T8									
Total										

Proportion of observed agreement:

$$P_a = \frac{1}{n} \sum_{i=1}^p n_{ii}$$

Theoretical proportion of observed agreement:

$$P_e = \frac{1}{n^2} \sum_{i=1}^p n_{i.} \cdot n_{.i}$$

Kappa :

$$\kappa = \frac{P_a - P_e}{1 - P_e}$$

The Kappa index will be calculated for the global population, the population where the clinical diagnosis is « strongly certain/certain » and « strongly uncertain/uncertain » and the population with a CT-scan < 12h.

8.2.4. Proportion of cases when the chest physiotherapy protocol is modified following the results of the LUS:

Calculation of proportion: $P_{\text{upevents}} + P_{\text{upnonevents}}$ for all of the clinical hypothesis, for each clinical hypothesis and in the CT-scan <12h subpopulation.

With a confidence interval at $\alpha=0.05$.

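### Section 8.2.4 adds two rates with different denominators, so the reported frequency of modified physiotherapy protocols is overstated and can exceed 100%

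*Combined protocol and SAP*

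**What the plan says.** Secondary objective 3 (section 3.2) is to "Determine the frequency of changes in the chest physiotherapy following the assessment of the LUS results", overall and by clinical hypothesis. The matching secondary criterion 3 (section 4.2) is the "Proportion of cases when the chest physiotherapy protocol is modified following the results of the LUS", and it adds the subgroup with a CT scan under 12 hours old.

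Section 8.2.4 sets out the estimate: "Calculation of proportion: $P_{\text{upevents}} + P_{\text{upnonevents}}$ for all of the clinical hypothesis". It applies the same expression to each hypothesis and to the CT subgroup, with a confidence interval at α = 0.05. It does not redefine the two terms.

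The terms come from section 8.2.1:

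- P_upevents is the "number of «events» when the LUS results modified the chest physiotherapy treatment modalities divided by the total number of «events".
- P_upnonevents is the "number of «non-events» when the LUS results modified the chest physiotherapy treatment modalities divided by the total number of «non-events".

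The two groups are complements of each other. A case counts as an event when ultrasound fits the clinical diagnosis; otherwise it falls in the second group, defined as "Non Events: the results of the lung and diaphragm US are not compatible with the clinical diagnosis for a clinical hypothesis".

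For the intensivist, objective 4 is to "Determine the frequency of changes in the medical treatment (determined by intensivist"), while section 8.2.5 specifies only an NRI.

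**The concern.** Each term is a rate within its own group. A sum of two within-group rates can run from 0 to 2 and is not the share of all cases that criterion 3 names. The expression would be right only if both terms were divided by all cases. That contradicts the definitions in 8.2.1 and the primary z-test, which uses each group's own count. The plan does write a common denominator where it wants one: observed agreement for kappa in 8.2.3 is divided by the overall n.

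This is the only pooled figure in the plan for how often ultrasound changes chest physiotherapy. The NRI cannot stand in for it. As defined in 8.2.1, P_down = 1 − P_up in each group, so NRI = 2 × (P_upevents − P_upnonevents). Modification rates of 10% and 25% give an NRI of −30%, and so do rates of 60% and 75%.

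The error also runs in the direction of the research hypothesis (section 2) that ultrasound changes decisions. Section 10 makes a later randomised trial depend on positive results.

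**Working it through.** **Inputs.** Let E be the number of compatible cases and M the number of non-compatible cases (definitions in 8.2.1), with N = E + M. Let a and b be the numbers modified in each, p_e = a/E, p_ne = b/M and w = E/N. Section 8.1 gives N = 150 and a target of at least 50 modifications. The plan gives neither the split between E and M nor the modification rate in each group, so every split and rate below is an assumption.

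**The plan's own figure.** No value is stated for the 8.2.4 proportion. The nearest is 50 modifications in 150 patients, or 33.3%. (The expected 30% in 8.1 would give 50/0.30 = 167 patients, not 150. That is a separate matter and does not affect this point.)

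**Formulas.**

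- Section 8.2.4: S = p_e + p_ne
- Share of all cases: T = (a + b)/N = w·p_e + (1 − w)·p_ne
- Excess: S − T = (1 − w)·p_e + w·p_ne

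The excess is never negative. With both groups non-empty it is zero only when nothing is modified. With w = 0.5, S = 2T exactly.

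**Examples with N = 150.**

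| Compatible (modified) | Non-compatible (modified) | Section 8.2.4 sum | True proportion |
|---|---|---|---|
| 75 (15) | 75 (35) | 15/75 + 35/75 = 66.7% | 50/150 = 33.3% |
| 100 (20) | 50 (30) | 20/100 + 30/50 = 80.0% | 50/150 = 33.3% |
| 100 (10) | 50 (40) | 10/100 + 40/50 = 90.0% | 50/150 = 33.3% |
| 120 (22) | 30 (28) | 22/120 + 28/30 = 111.7% | 50/150 = 33.3% |
| 100 (20) | 50 (40) | 20/100 + 40/50 = 100% | 60/150 = 40.0% |
| 75 (15) | 75 (60) | 15/75 + 60/75 = 100% | 75/150 = 50.0% |
| 100 (30) | 50 (45) | 30/100 + 45/50 = 120% | 75/150 = 50.0% |

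In the first four rows the number modified is the same and the true figure does not move. The reported figure changes with the split alone. For 50/150 an approximate 95% interval is 0.333 ± 1.96 × √(0.333 × 0.667/150), or 25.8% to 40.9%. All four sums lie above it.

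**Under the plan's expectations.** Take an NRI of 30% in absolute value, which means a 15-point gap between the groups, and 50 of 150 modified.

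- Event share 30%, non-events the higher group: p_e = 0.333 − 0.15 × 0.7 = 22.8%, p_ne = 37.8%, S = 60.7%.
- Event share 50%: S = 66.7%.
- Event share 70%, non-events the higher group: p_e = 0.333 − 0.15 × 0.3 = 28.8%, p_ne = 43.8%, S = 72.7%.

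Reversing the sign of the NRI gives the same range, 60.7% to 72.7%, against a true 33.3%.

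**All possible tables.** Counting every table with N = 150 and both groups non-empty gives 584,974. The sum is below the true proportion in none. It equals it in 149, all with no modification. Otherwise the ratio S/T runs from 1.007 (E = 149, only compatible cases modified: 150/149) to 150 (the single case in a group of one is the only one modified).

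**Empty groups.** If a hypothesis or the CT subgroup has no compatible or no non-compatible case, one term is 0/0 and the 8.2.4 estimate is undefined. The true proportion is still computable.

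**The case against.** The strongest points on the other side are these:

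- **Intent and reach.** The heading of 8.2.4 and criterion 3 make the intended quantity clear, the data are unaffected, and a careful statistician would probably divide by all cases without being told. It is a secondary, descriptive estimate; the primary NRI and the sample size do not use it. This bears on how far the error reaches. The written rule is still wrong, a silent correction would depart from the plan, and a wrong value below 100% gives no warning.
- **Always overstated.** This is too strong. With no modification both figures are zero, and with an empty group the sum is undefined. That stands, and the conclusion is worded accordingly.
- **Confidence interval.** No method is named, and a valid interval for a sum of two proportions can be built. True, but it would cover the wrong quantity, and an ordinary binomial interval does not apply to the sum.
- **Values above 100%.** At 50 modifications in 150 they need an uneven table. This stands: under the plan's expectations the more typical result is about double the truth.
- **Unit of analysis.** Section 8.2.1 speaks of a clinical hypothesis, and 6.5.1.4 allows several per patient. If hypotheses were the unit, observations within a patient would be correlated and a simple interval would fail. However, 6.5.1.5 and 7.4.3 define the treatment modalities for the primary hypothesis only, so one before-and-after comparison per patient is the natural unit. The plan should say so.
- **Intensivist analysis.** Criterion 4 is worded as modification of the decision, not as a proportion, so 8.2.5 does follow its criterion. The gap is between objective 4 and the analysis. It is a lesser, separate omission, but a real one.

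**Conclusion.** The formula in 8.2.4 is wrong as written. It overstates the frequency of modified protocols whenever at least one protocol is modified and both groups contain cases. It gives exactly twice the truth when the groups are equal and can exceed 100%. At the plan's target of 50 in 150, the true figure is 33.3%. The formula gives 60.7% to 72.7% if the NRI is 30% in absolute value and the event share lies between 30% and 70%, and up to 111.7% in the uneven example shown. The sizes rest on assumed splits and rates; the direction does not.

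The overall, by-hypothesis and CT-subgroup estimates are all affected. The primary NRI is not. As a smaller matter, the frequency of medical-treatment changes asked for in objective 4 is not computed in 8.2.5, because an NRI fixes only the difference between two rates and not their level.

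**What to change.** 1. In 8.2.4, replace the sum with (modified compatible cases + modified non-compatible cases) / (all compatible + all non-compatible cases). Use it overall, by hypothesis and in the subgroup with a CT scan under 12 hours old.
2. State that the unit is the patient, classified by primary hypothesis, in line with 6.5.1.5 and 7.4.3.
3. Name the interval: Wilson or exact binomial, 95%. If the sponsor wants every hypothesis counted separately, the interval must allow for several hypotheses per patient.
4. Report P_upevents and P_upnonevents separately, each with its own denominator, so that readers can see where the modifications occur.
5. In 8.2.5, add the same pooled proportion for changes in medical treatment, overall and by hypothesis, so that objective 4 is answered.

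The cost is one corrected formula, a sentence on the unit, and one added proportion. Sections 7.4.2 to 7.4.5 already provide for the treatment plans before and after ultrasound to be recorded, so no new data or patients are needed. For the same data, the reported frequency will be lower than the present formula would give.

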8.2.5. Modification of the intensivist clinical decision

Calculation of the net reclassification index (NRI):

$$\text{NRI (\%)} = (P_{\text{upevents-I}} - P_{\text{downevents-I}}) - (P_{\text{upnonevents-I}} - P_{\text{downnonevents-I}})$$

With:

Events: the results of the lung and diaphragm US are compatible with the medical diagnosis of intensivist for the patient respiratory condition for a clinical hypothesis.

Non Events: the results of the lung and diaphragm US are not compatible with the medical diagnosis of intensivist for the patient respiratory condition for a clinical hypothesis.

P_{upevents}: number of «events» when the LUS results modified the medical treatment for the patient respiratory condition divided by the total number of «events».

P_{downevents}: number of «events» when the LUS results didn't modify the medical treatment for the patient respiratory condition divided by the total number of «events».

P_{upnonevents}: number of «non-events» when the LUS results modified the medical treatment for the patient respiratory condition divided by the total number of «non-events».

P_{downnonevents}: number of «non-events» when the LUS results didn't modify the medical treatment for the patient respiratory condition divided by the total number of «non-events».

9. Justification for current care

Lung and diaphragm US is a diagnostic tool used in routine practice in ICUs by predominantly physicians. It has been validated as a tool to screen for pulmonary consolidation, atelectasis, interstitial syndrome, pleural effusion, pneumothorax and diaphragm dysfunction (16,30). The sensitivity and specificity of LUS are greater than those for chest X-ray at diagnosing these diseases in patients hospitalized in ICUs who present signs of acute respiratory failure (hypoxemia). LUS is non-invasive, painless and does not involve radiation. There are no contra-indications and no adverse side effects. We expect that LUS findings may lead to a modification in decisions concerning chest physiotherapy by both the physiotherapist and the physicians. The choice of the chest physiotherapy and medical treatment protocol are made by the physiotherapist and physician, respectively, in charge of the patient and is based on the clinical assessments and clinical parameters available and according to the benefit/risk ratio. Usually, the availability of these elements varies depends on the clinical situation and physiotherapist and physician establish their treatment plan or may decide not to intervene if treatment is not indicated or could have increased patient risk. The addition of a lung and diaphragm US will not modify this choice based on the patient's

safety. Moreover, the chest physiotherapy techniques and medical treatment used are those conventionally used.

10. Expected benefits for patients

We expect that decisions for chest physiotherapy may be modified when the physiotherapist and intensivist have access to the results of lung and diaphragm US as well as the usual clinical and imaging parameters.

The sensitivity and specificity of LUS is greater than that for the tools usually used by intensivists and physiotherapists (auscultation, chest X-ray, clinical examination) to explore respiratory dysfunction and to determine indications for chest physiotherapy. LUS may affect the management of patients with regard to chest physiotherapy by providing a more precise evaluation of the respiratory status and should lead to a more appropriate chest physiotherapy treatment.

The expected benefit for patients is therefore that they will be given a chest physiotherapy protocol that is better suited to the type of respiratory dysfunction. This may include more optimal physiotherapy techniques for the patient, the decision not to intervene if physiotherapy is not indicated and more effective referral to the ICU physician in cases of doubt or suspicion of a condition that may warrant physician intervention.

If the results of this investigation are positive, we plan to conduct another randomised controlled trial, with patients allocated to chest physiotherapy guided by lung ultrasound or clinical examination alone, with the objective to evaluate the impact of the use of LUS on respiratory function, time on mechanical ventilation, mortality rates and hospital length of stay).

11. Risks for patients taking part in the study

No additional treatment or diagnostic studies are administered as part of this study. The lung and diaphragm US will be performed via the trans-thoracic approach. The examination is therefore non-invasive, completely painless and requires no exposure to radiation.

13. Funding

This study will be funded by the CHU de Dijon, the Forcilles' hospital and the Paris St Joseph Hospital Network for the French centre and by the University of Technology Sydney for the Australian centre. Funding will cover the time spent by the physiotherapist doing the LUS-scans, the time spent by the clinical research technician to collect the data, and by the CRA to monitor the study and take part in the statistical analysis.

14. Data recording in the Case Report Form

All of the data will be recorded in an e-CRF (<https://projectredcap.org>) and will be available for each investigator. All data will be anonymised.

15. Ethical and regulatory aspects

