6.5.1.4. Clinical hypotheses

Following the examination, he/she will put forward one or several hypotheses concerning the respiratory dysfunction (and not the medical diagnosis) and will either confirm or refute the indications for chest physiotherapy (*cf. annexe 2a*). If chest physiotherapy is indicated, the physiotherapist will specify the protocol to be used. The choice of the treatment modalities with regard to the type of respiratory dysfunction is detailed in annexe 2b.

According to the clinical examination, the clinical physiotherapist formulates one or more of the following clinical hypothesis (*cf annexe 2a*):

- Clinical examination is compatible with retained airway secretions;
- Clinical examination is compatible with bronchospasm;

- Clinical examination is compatible with pneumonia/consolidation;
- Clinical examination is compatible with atelectasis (~~passive or obstructive~~active mechanism);
-
- Clinical examination is compatible with pleural effusion;
- Clinical examination is compatible with pulmonary edema or global interstitial syndrome;
- Clinical examination is compatible with pneumothorax;
- Clinical examination is compatible with reduced aeration at the most dependent parts of the lungs;
- Clinical examination is compatible with unilateral diaphragm dysfunction (~~unilateral or bilateral~~);
- Clinical examination is compatible with bilateral diaphragm dysfunction;
- Clinical examination is inconclusive.

Among the formulated clinical hypotheses, the clinical physiotherapist will choose one primary clinical hypothesis (the choice is left to the discretion of the clinical physiotherapist, based on the probability and priority of the clinical hypothesis in terms of treatment).

A lung and diaphragm US will be done (see below) following the evaluation of the clinical physiotherapist with the physiotherapist who undertakes the US assessment blinded to the clinical assessment findings of the clinical physiotherapist. The clinical physiotherapist will then incorporate the results of the lung and diaphragm US and deem whether they are compatible with the clinical hypotheses put forward. He/she will then specify the chest physiotherapy protocol according to the results of the US-scan.

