The basics lung ultrasound semiology is described in annexe 3b. The following syndromes will be searched for: normal profile, alveolar-interstitial syndrome, pulmonary consolidation, pleural effusion, pneumothorax and diaphragm dysfunction (16).

The ultrasound syndromes are defined by the following signs in a scanned for the in six-lung zones of each chest wall of the patient:

Normal lung:

- Bat sign;
- A lines;
- Pleural sliding (seashore sign).

A normal profile is compatible with presence of tracheo-bronchial retained secretions and bronchospasm.

Alveolar-interstitial syndrome(16–18):

- A positive region is defined by the presence of three or more B-lines in a longitudinal plane between two ribs;
- In the anterior and lateral thoracic areas;
- Multiple and well-defined B-lines: moderate loss of lung aeration;
- Confluent B-lines: severe loss of lung aeration.

The presence of a focal sonographic pattern of interstitial syndrome is compatible with pneumonia, atelectasis or pulmonary contusion.

The presence of multiple diffuse bilateral B-lines is compatible with pulmonary oedema or ARDS. In the case of pulmonary oedema, the interstitial syndrome is diffuse, homogeneous and bilateral. In the case of ARDS, the interstitial syndrome is diffuse, heterogeneous, bilateral and associated with pleural abnormalities and sub-pleural consolidations.

Lung consolidation:

- Subpleural echo-poor region or tissue-like echo-structure;
- Atelectasis pattern(19,20):

- Abolished pleural sliding;
 - Static air bronchogram;
 - Lung pulse;
 - Passive atelectasis due to compression from the surrounding pleural effusion: homogeneous echogenic structure into the pleural effusion, with smooth margin and linear air bronchogram(21).
- Pneumonia pattern(22–25):
- Irregular deep margin when the consolidation is partial;
 - Regular deep margin when consolidation involves an entire lobe;
 - Static or dynamic air bronchogram;
 - Fluid bronchogram;
 - Vascular pattern;
 - Bilateral or unilateral.

The aim of physiotherapist is not to identify the medical diagnosis. Regarding the presence of the interstitial syndrome and lung consolidation, the aim is to also define the level of lung aeration present in each of the 12 lung zones:

- Normal aeration (N): presence of lung sliding with A-lines or fewer than two isolated B-lines;
- Moderate loss of lung aeration (B1): multiple, well-defined B-lines (B1 lines);

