7.4.2. Inclusion visit

The following data will be collected:

- Demographic: age, sex, size, weight, BMI, smoking, alcohol consumption, history of cirrhosis, diabetes or a chronic respiratory disease, heart failure;
- Reason for hospitalization:
 - Chronic respiratory disease decompensation : COPD, obesity hypoventilation, restrictive lung disease;
 - Acute severe asthma;
 - Community-acquired and hospital-acquired pneumonia;
 - ARDS;
 - Acute respiratory distress: infection, acute pulmonary edema, other identified causes, other non identified causes.
 - Pulmonary embolism;
 - Post-operative (urologic, digestive, vascular, and thoracic surgery);
 - Sepsis;
 - Coma;
 - Acute heart failure;
 - Multi-organ failure;
 - Cancer;
 - Continuous monitoring;
 - Other (detail).

- Medical diagnosis and medical treatment planned of hypoxemia (or cause of hypoxemia).

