7.4.5. LUS reporting to clinical physiotherapist and intensivist

The clinical physiotherapist and intensivist reviews the LUS report. Taking into account these LUS report, the clinical physiotherapist once again selects the chest physiotherapy treatment modalities indicated. The second chest physiotherapy treatment modalities will be recorded, with the reasons for a change of interventions (if indicated). The intensivist will again review any medical decisions that have been made. The new medical treatment for hypoxemia (or cause of hypoxemia) is recorded.

7.4.6. Second visit of the clinician physiotherapist: implementation of the chest physiotherapy treatment

After the review of the LUS report, the clinical physiotherapist may or may not decide to perform the chest physiotherapy treatment, to refer the patient to the intensivist, dependent upon his/her therapeutic strategy choice. The executed chest physiotherapy treatment provided will be recorded. The following data will be recorded:

- Current medical management:
 - o Oxygen therapy (and flow);
 - o Mechanical ventilation, NIV (PEEP, IPAP);
- Severity score: SOFA
- Vital signs: RR, HR, BP SpO₂, FiO₂ (true or estimated), body temperature, RASS, Glasgow coma score;
- Adverse effects during the chest physiotherapy treatment:
 - o Desaturation (< 4% of initial SpO₂);
 - o Decrease or increase of blood pressure (> 20% of initial SBP or DBP);
 - o Decrease or increase of heart rate (> 20% of initial heart rate);
 - o Endotracheal tube removal;
 - o Catheter or perfusion removal.

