7.4.8. Patient follow-up synthesis

	Pre-inclusion J 0	Inclusion J 0	First clinical physiotherapist visit J 0	LUS J 0	LUS results reading by the clinical physiotherapist and intensivist J 0	Second clinical physiotherapist visit J 0	End- research visit
Information consent	✓						
Demographic data		✓					
Reason for hospitalization, medical diagnosis if different		✓					
Medical management			✓			✓	
SAPSOFA , vital signs			✓			✓	
Medical diagnostic for respiratory condition		✓					
Medical treatment planned for respiratory condition		✓					
Clinical hypotheses of the clinical physiotherapist			✓		✓		
Choice of chest physiotherapy protocol			✓		✓		
LUS scan				✓			
LUS-scan report				✓	✓		
New choice of chest physiotherapy protocol						✓	
Adverse effect recording						✓	
New medical treatment planned for hypoxemia					✓		
ICU length of stay, duration of MV, vital status							✓

The data will then be entered in an e-CRF (Redcap.com) and analysed at the St. Joseph Hospital Network.

The statistical analysis will be conducted by the Clinical Research Centre (CRC) of the St. Joseph Hospital Network. An identifier will be attributed to each patient (initials of first name and family name – year of birth) and the data will be entered on an EXCEL file, which will be sent to the statistician in charge of the analysis at the St. Joseph Hospital Network.

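### The intensivist reclassification index in section 8.2.5 needs a compatibility status that the protocol neither defines nor describes as recorded, and it has no category for diagnoses that ultrasound cannot test

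*Combined protocol and SAP*

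**What the plan says.** Section 8.2.5 applies the physiotherapist's index to the intensivist. A patient is an event when the ultrasound is "compatible with the medical diagnosis of intensivist for the patient respiratory condition for a clinical hypothesis", and a non-event when it is not. Within each group, up means that medical treatment was modified after the scan and down means that it was not.

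The sections that feed this definition say the following.

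- **Hypotheses (6.5.1.4).** These are formulated by the clinical physiotherapist from a list of 11 items. They are "hypotheses concerning the respiratory dysfunction (and not the medical diagnosis"). The physiotherapist must then judge the scan against them and "deem whether they are compatible with the clinical hypotheses put forward".
- **Intensivist, before the scan (7.4.2).** The item is "Medical diagnosis and medical treatment planned of hypoxemia (or cause of hypoxemia"). It has no category list. The list of admission reasons in the same section is a separate item. In the schedule (7.4.8), the row "Medical diagnostic for respiratory condition" is ticked once, at inclusion.
- **Intensivist, after the scan (7.4.5).** "The intensivist will again review any medical decisions that have been made", and "The new medical treatment for hypoxemia (or cause of hypoxemia) is recorded".
- **Aim of the scan (6.5.2.3).** "The aim of physiotherapist is not to identify the medical diagnosis".

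**The concern.** The index needs two facts per patient: whether treatment changed, and whether the scan fitted the intensivist's diagnosis. The protocol describes collection of the first but not of the second. The qualifier that ties compatibility to a clinical hypothesis has nothing to refer to on the intensivist's side, because only the physiotherapist formulates hypotheses.

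Two things are at stake. First, if someone fills in compatibility after the data are complete, that person can see whether treatment changed, so the grouping variable can drift towards the outcome. Second, the split is binary. A diagnosis on which ultrasound is silent, such as pulmonary embolism if that is what was recorded as the cause of hypoxemia, must be forced to one side. Section 8.2.3 handles the same difficulty for kappa by removing retained secretions and bronchospasm, which ultrasound cannot diagnose. Section 8.2.5 has no such provision.

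A further ambiguity is that objective 4 and criterion 4 ask for results by type of clinical hypothesis without saying whose hypothesis is meant.

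**Working it through.** **Plan's own figure.** The plan gives no expected value or precision for the intensivist index. Section 8.1 sizes the study (150 patients) on the physiotherapist index only, so there is nothing to reproduce here. Only the 150 is used below.

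**Step 1: trace each term of 8.2.5 to its source.**

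| Term needed | Physiotherapist | Intensivist |
|---|---|---|
| Starting hypothesis | 6.5.1.4 and 7.4.3, 11-item list, one primary | None described |
| Starting diagnosis | Same as above | 7.4.2, no categories |
| Ultrasound diagnosis | 7.4.4, Annexe 4 | Same |
| Compatibility judgement | 6.5.1.4 | None described in 7.4.2 to 7.4.5, 7.4.8 or Annexe 4 |
| Treatment before and after | 7.4.3 and 7.4.5 | 7.4.2 and 7.4.5 |

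The treatment-change axis is complete for both clinicians. The compatibility axis is described for the physiotherapist only. Section 6.5.1.3 also allows for a working medical diagnosis not yet having been made, and 8.2.5 has no rule for that case.

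**Step 2: how much of the index depends on event status.** Up and down sum to 1 within each group. With p_e and p_n the proportions modified among events and non-events:

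index = (2p_e − 1) − (2p_n − 1) = 2(p_e − p_n).

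Both proportions need event status, so no part of the index survives without it. The overall proportion of patients with modified treatment does not need it.

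**Step 3: sensitivity, on assumed counts.** The documents give no such counts. Assume 150 patients: 90 true events with 13 modified and 60 true non-events with 32 modified (45 of 150, 30%, modified overall). The index is 2(13/90 − 32/60) = −77.8%. It is negative only because change is assumed to be commoner when the scan disagrees. Now let the status of 10% to 50% be undetermined, drawn in proportion from both groups (rounded).

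| Undetermined (modified) | Left with status: events; non-events | Left out | All coded events | All coded non-events | Status follows outcome: lowest to highest |
|---|---|---|---|---|---|
| 15 (4) | 12/81; 29/54 | −77.8% | −74.1% | −66.0% | −87.7% to −51.6% |
| 30 (9) | 10/72; 26/48 | −80.6% | −71.1% | −62.0% | −101.3% to −28.4% |
| 45 (14) | 9/63; 22/42 | −76.2% | −62.2% | −54.2% | −109.4% to −0.5% |
| 75 (23) | 6/45; 16/30 | −80.0% | −58.3% | −47.6% | −134.8% to +46.3% |

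Example, second row. Left out: 2(10/72 − 26/48) = −80.6%. All coded events: 2(19/102 − 26/48) = −71.1%. All coded non-events: 2(10/72 − 35/78) = −62.0%. Lowest, with the 9 modified called non-events and the 21 unmodified called events: 2(10/93 − 35/57) = −101.3%. Highest, the reverse: 2(19/81 − 26/69) = −28.4%.

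The last column is an outer bound, not a forecast. It shows that the main exposure is coding that follows the outcome, and that coding everyone to one side moves the index much less.

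**The case against.** The strongest reply is that the raw material is on file. The pre-scan diagnosis and the ultrasound diagnosis are both recorded, and section 6.5.2.3 links ultrasound patterns to pneumonia, pulmonary oedema and ARDS. For those patients compatibility can be worked out. Compatibility is also a weaker demand than identification, so the statement that the scan does not aim at the medical diagnosis does not by itself defeat the endpoint. All of this stands. What remains missing is the rule, the assessor, blinding to the treatment change, and a place for untestable diagnoses.

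Several stronger readings are tempting but unsupported.

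- **That criterion 4 cannot be derived at all.** Planned and new treatment are both recorded, so the frequency of change is available overall and by the physiotherapist's hypothesis.
- **That many patients are unclassifiable.** A reader might infer this from admission reasons such as sepsis, severe asthma or COPD decompensation. Those are reasons for hospitalisation; the diagnosis of hypoxemia is a separate item. Section 6.5.2.3 also treats a normal profile as compatible with bronchospasm, which gives asthma a link.
- **That compatibility is certainly not collected.** The case report form is not among the documents. The safe statement is that the protocol does not describe it.
- **That grouping by the physiotherapist's hypothesis is wrong.** It is a coherent subgroup, provided the plan says that this is what is meant.
- **That the distortion is known to be large.** Take 14/70 events and 20/50 non-events modified (index −40%), with 30 more patients unclassified. If 9 of the 30 are modified, coding all as events gives 2(23/100 − 20/50) = −34.0% and all as non-events gives 2(14/70 − 29/80) = −32.5%. A spread of about 53 points (−10.0% against −62.5%) appears only if 21 of the 30 are modified, and nothing in the documents suggests that.

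**Conclusion.** The point holds for the intensivist index in 8.2.5 and for any breakdown by the intensivist's own starting hypothesis. It does not extend to the frequency of medical treatment changes in objective 4, nor to the physiotherapist index, for which 6.5.1.4 describes a compatibility judgement.

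This is more than loose wording. Followed as written, event status would be assigned after the fact with the outcome visible, and untestable diagnoses would have to be pushed into one of two groups. The size is unknown because the share of unassessable patients is not given; the table rests wholly on assumed counts. Because this is a secondary analysis in a self-described pilot, it should be corrected, but it does not threaten the primary result.

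**What to change.** 1. **Section 7.4.2.** Alongside the medical diagnosis, have the intensivist tick the suspected respiratory dysfunction(s) from the 6.5.1.4 list, with one marked as primary.
2. **Section 7.4.5.** Record compatible / not compatible / not assessable before the new treatment is entered, and name who makes the judgement. Alternatively, derive it from a mapping to the Annexe 4 diagnoses that is fixed before analysis and applied blind to treatment change. The mapping has to be written: the protocol states none for the physiotherapist that could be reused. The blind mapping separates status from outcome more firmly, since the intensivist who judges compatibility also decides treatment. It is also the only one of the two routes left if inclusion is already complete.
3. **Section 8.2.5.** Compute the index on assessable patients. Report the not-assessable stratum separately, with its number and its proportion with changed treatment.
4. **Objective 4 and criterion 4.** State whether the clinical hypothesis used for grouping is the intensivist's or the physiotherapist's.

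The cost is one short form item for a clinician whose diagnosis and treatment decisions are already being recorded, some SAP wording, and fewer patients in the index.
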